9.4 Safety

Safety of the therapy will be assessed by comparing the incidence of adverse events in the MONOVISC vs. Saline group through 26 Weeks post-injection, including AEs that occur during injection.

10 Hypotheses

The primary endpoint analysis will be conducted to demonstrate that the mean WOMAC A1 walking pain score change from baseline for MONOVISC is significantly better than the mean WOMAC A1 walking pain score change from baseline for Saline at 26 Weeks after the first injection. The null (H_0) and alternate (H_A) hypotheses for this test of superiority are as follows:

$$H_0: \mu_{\text{MONOVISC}} \geq \mu_{\text{Saline}}$$

$$H_A: \mu_{\text{MONOVISC}} < \mu_{\text{Saline}},$$

where μ_{MONOVISC} is the mean WOMAC A1 walking pain score change from baseline for MONOVISC at 26 Weeks, and μ_{Saline} is the mean WOMAC A1 walking pain score change from baseline for Saline at 26 Weeks.

Decision Criterion: The primary endpoint analysis will be based upon a longitudinal model as described in Section 13.4.1. The adjusted means from this longitudinal model at 26 Weeks will be compared between treatment groups. The decision will be made to reject the null hypotheses and conclude the alternative if:

1. WOMAC A1 walking pain change from baseline adjusted mean for the MONOVISC group is less than the WOMAC A1 walking pain change from baseline adjusted mean for the Saline group and,
2. The two sided p-value for the comparison of these adjusted means is less than 0.05. Or, equivalently, if the entire 2-sided 95% confidence interval for the WOMAC A1 walking pain change from baseline adjusted mean between treatment group difference (MONOVISC minus Saline), based upon the longitudinal model estimates, is less than 0.

11 Analysis Sets

A detailed accounting of all enrolled Subjects will be documented with the following analysis sets.

Intent to Treat (ITT) Analysis Set: The ITT Analysis Set consists of all subjects who are enrolled into the study. Subjects in the ITT Analysis Set but in whom treatment is not attempted with either MONOVISC or Saline will be listed along with the reason for not being treated.

Safety Analysis Set: The Safety Analysis Set consists of all randomized subjects who were enrolled into the study and in whom treatment was attempted with either MONOVISC or Saline. Subjects will be analyzed according to the treatment which was attempted.

As Treated (AT) Analysis Set for Each Follow-up Time Point: For each follow-up time point (the 2, 4, 8, 16 and 26 Week visits), the AT Analysis Set will consist of all Safety Analysis Set subjects who have a follow-up visit within the interval (see Table 2) in which WOMAC A1 walking pain data was to have been collected. Reasons for not having a WOMAC A1 walking pain result in the interval will be documented (including deaths, withdrawals of consent, and Subjects who are past due for follow-up in the interval). Subjects will be analyzed according to the treatment which was administered.

[figure not shown]
Modified Intent to Treat (MITT) Analysis Set (for Longitudinal Analysis): All primary endpoint data from all MITT Analysis Sets for Each Follow-up Time Point will be combined into a dataset for the purpose of longitudinal analysis of the primary and secondary endpoints. In this MITT Analysis Set, primary endpoint data for the 26 Week visit will be imputed with multiple imputation methodology. Subjects will be analyzed according to the treatment which was administered.

Per Protocol (PP) Analysis Set for Each Follow-up Time Point: The PP Analysis Set for each follow-up time point (the 2, 4, 8, 16 and 26 Week visits) will consist of the subjects included in AT Analysis Set for Each Time Point, excluding subjects with major protocol violations (i.e., those which are deemed to have possibly affected the scientific validity of the data). The intent is to assess inclusion of each subject at each time point independently, based upon the subject's protocol deviations. A deviation may have a transitory effect on the endpoint (e.g., use of acetaminophen within 48 hours prior to a study visit) and therefore a single time point may be impacted as opposed to study-level violations, like unmet inclusion/exclusion criterion.

Per Protocol Analysis Set for Longitudinal Analysis: All primary endpoint data from all PP Analysis Sets for Each Follow-up Time Point will be combined into a dataset for the purpose of longitudinal analysis of the primary endpoint. No PP Analysis of the Secondary endpoints will be conducted.

For each follow-up time point (the 2, 4, 8, 16 and 26 Week visits), a flowchart, as shown in Figure 2, will be created. The flowchart will present the Safety Analysis Set, the As Treated Analysis Set, and the Per Protocol Analysis Set for the Time Point. This diagram will indicate all protocol violations, deaths, withdrawals of consent, and Subjects who are past due for follow-up in the interval.

Figure 2 Example of Analysis Set Flow for a Specific Time Point

A Medically Trained Professional and a Biostatistician at DePuy Synthes will review and confirm all protocol non-compliances prior to the IA data cut, and also prior to Final dataset lock. The Analysis Sets constructed for the IA will be designated as “IA” as they will differ from the Final (end of study) Analysis Sets.

12 Sample Size Justification

The sample size was determined based on the primary endpoint, which is a superiority comparison of WOMAC A1 walking pain change from baseline at 26 Weeks for MONOVISC Subjects compared to Saline Subjects. Although it is planned to conduct the primary endpoint analysis with a longitudinal model, and to compare the WOMAC A1 walking pain change from baseline adjusted means at 26 Weeks from this longitudinal model, the sample size was established based upon estimates for a t-test comparison of 26 week means for simplicity.

Specifically, it is anticipated that the mean difference in WOMAC A1 walking pain change from baseline means will be at least 0.6 (where the mean for MONOVISC subjects is less than the mean for Saline Subjects), and that the standard deviation in WOMAC A1 walking pain change from baseline at 26 weeks will be approximately 2.2 in both groups. This standard deviation of 2.2 is consistent with published studies by Spitzer (2010)² and Qvistgaard (2006)³; also, 2.2 is approximately ¼ of the maximum anticipated range of WOMAC A1 walking pain change from baseline, which would be an estimate of the standard deviation from data which are normally distributed. Using a two-tailed t-test and assuming a 2:1 randomization, the required sample size to yield 80% statistical power was estimated to be 318 MONOVISC and 159 Saline. With an anticipated attrition rate of 15%, the total study population was increased to be 560 patients (374 MONOVISC, 186 Saline). The sample size estimate was calculated with the following SAS code.

Figure 3 SAS Code for Power Estimation: WOCAC A Pain at 26 Weeks

```
proc power;
  twosamplemeans
  meandiff= .6
  stddev=2.2
  groupweights=(2 1)
  power= .8
  alpha=0.05
```

13 Analysis Plan

All statistical processing will be performed using SAS® Version 9.2 or higher, unless otherwise noted.

Descriptive statistics for dichotomous/categorical variables will include the number and percentage of subjects. Fisher's exact test 2-sided p-values will be provided for the comparison of dichotomous variables, including adverse event rates, to facilitate clinical judgment. Descriptive statistics for continuous variables will include the number of subjects, mean, standard deviation, median, minimum, and maximum. P-values for comparing continuous endpoints will be provided to facilitate clinical judgment; these will be 2-sided p-values based upon the t-distribution.

Summary tables will be provided for subject demographics and baseline variables for the Safety Analysis Set, the As Treated Analysis Set at 26 Weeks, and the Per Protocol Analysis Set at 26 Weeks. Safety endpoints (adverse events) will be summarized on the Safety Analysis Set. Effectiveness endpoints will be summarized at each protocol-specified evaluation time point on the Per Protocol Analysis Set for the time point. Analyses will be conducted on pooled data from all sites unless the analysis described in Section 13.7 determines sites are not poolable.

13.1 General Reporting Conventions

After all subjects have completed the primary endpoint (26 week) follow-up visit, a clinical study report will be provided to FDA for review. Trial results will also be posted on www.clinicaltrials.gov.

13.2 Subject Disposition/Patient Accountability

In addition to the Analysis Set Flowcharts as described in Section 11, the number and percentage of subjects in the following categories will be tabulated and presented by treatment group:

- Enrolled (ITT);
- Randomized;
- Safety Set;
- MITT Analysis Set for Longitudinal Analysis;
- PP Analysis Set for Longitudinal Analysis;
- MITT Analysis Set for Each Time Point;
- PP Analysis Set for Each Time Point;
- Completed Treatment;
- Completed Study Visits (2, 4, 8, 16 and 26 Week);
- Prematurely discontinued the study and the reason for discontinuation.

The disposition summary will be based on all subjects and discontinuation analysis will be based on the MITT.

13.3 Demographic and Baseline Characteristics

Summary tables will be provided for subject demographics and important baseline variables for the Safety Analysis Set, the As Treated Analysis Set at 26 weeks, and the Per Protocol Analysis Set at 26 weeks.

13.4 Efficacy Evaluations

13.4.1 Primary Endpoint Analyses

The primary endpoint analysis will be conducted with a longitudinal model on the MITT Analysis Set using PROC MIXED. The model will include absolute change from baseline in WOMAC A1 as the dependent variable, treatment (MONOVISC versus Saline) and visit (Week 2, Week 4, Week 8, Week 16, and Week 26) as fixed effects, and subject as a random effect. In the model, visit will be treated as class variable and an antidependence covariance matrix will be assumed to model the within-subject variability between visits. The antidependence structure allows the correlation between different time periods to vary. Denominator degrees of freedom will be estimated using the Kenward–Roger approximation.

In order to test the robustness of study results to the antedependence model assumptions, the primary endpoint longitudinal analysis will be repeated with two additional covariance structures: autoregressive (AR) and Toeplitz. These analyses will be conducted on the same MITT analysis set which was utilized for the primary endpoint analysis.

With a mixed effects model as the primary analysis model, no imputation of missing data at visits prior to the Week 26 will be done. However, missing data at Week 26 will be imputed, as discussed in Section 8. A supportive analysis of the primary endpoint analysis will be conducted on the Per Protocol Analysis Set for Longitudinal Analysis with the same longitudinal model.

Age, Gender, and pre-injection WOMAC A1 pain score will be compared between treatment groups and if they are found to be significantly different ($p<0.05$) in the As Treated Analysis Set at 26 weeks, then an additional sensitivity analysis will be conducted for the primary endpoint analysis. In this analysis, fixed effects for Age, Gender, and the continuous baseline value of WOMAC A1 will be added, but otherwise the model will remain the same.

If marked differences are observed between the results obtained with the primary longitudinal model and any of the sensitivity analysis, they will be reported and addressed in the Clinical Study Report.

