	Radiographs are not collected post-baseline and will therefore not be summarized.....	24
13.5.3	Study Specific Data.....	24
13.6	Site Heterogeneity.....	24
13.7	Poolability Analysis	24
13.8	Additional Analyses.....	24
14	PLANS FOR INTERIM ANALYSIS (IA)	27
14.1	The Objectives of the IA.....	27
14.2	Efficacy and Safety Variables	27
14.3	Timing and Frequency of the IAs	27
14.4	Analysis sets for the IA.....	27
14.5	Data cut criteria	27
14.6	Analysis Plan	28
14.7	Possible Decisions or Actions Based on the IA Results	28
14.8	Statistical Approach for Modifying the Study Design	28
15	LIST OF TABLES, FIGURES, AND SUBJECT DATA LISTINGS.....	28
16	REFERENCES.....	28

1 List of Abbreviations

AE	Adverse Event
AT	As Treated
BSDM	Biostatistics and Data Management
CSP	Clinical Study Protocol
IA	Interim Analysis
IDE	Investigational Device Exemption
ITT	Intent-to-Treat
H_A	Alternative Hypothesis
H_0	Null Hypothesis
N/A	Not Applicable
NRS	Numerical Rating Scale
MITT	Modified Intent to Treat
OA	Osteoarthritis
PGA	Patient Global Assessment
PP	Per-Protocol
SAP	Statistical Analysis Plan
WOMAC	Western Ontario and McMaster Osteoarthritis Index

2 Modifications in Analysis from the Clinical Study Protocol

The basis of this SAP is the Clinical Study Protocol (CSP). For reasons of clarity certain redundant text has been omitted and changes have been made to address any typographical errors and improve consistency of terminology. In addition, substantive changes are presented in Table 1, below.

Table 1 Summary of Substantive Changes

Content	Modification	Justification
Block Randomization, stratified by study site	One Master Randomization List was created with which to sequentially label patient kits as MONOVISC or saline.	Stratification of randomization by study site was not feasible because it would have required a significant quantity of additional product, storage of randomized product by site, and added complexity in procedures with the supply vendor.
Mean Change from Baseline through 26 Weeks in WOMAC A1	Added endpoint and method of analysis	In addition to assessing the primary endpoint, WOMAC A1 walking pain

Content	Modification	Justification
		score change from baseline at 26 weeks, interest lies in assessing the difference in the mean change from baseline in WOMAC A1 over the entire study period.

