6.1 Control of Type 1 Error

Family-wise control of Type I Error across all primary and secondary endpoints will be accomplished using the following gatekeeping strategy which is depicted in Figure 1.

If the study is successful and the primary endpoint analysis demonstrates a statistically significant difference (favoring MONOVISC vs. Saline) at 26 Weeks, then we will test the WOMAC A1 change from baseline at 16 Weeks for a significant difference (favoring MONOVISC vs. Saline). If this is successful, we will test the difference at 8 Weeks; if this is successful, we will test the difference at 4 Weeks; and if this is successful, we will test the difference at 2 Weeks. At any point, if one of these comparisons fails to be statistically significant, then we will cease further testing in the specified order. Each of these tests will be conducted utilizing the primary endpoint analysis on the Modified Intent to Treat Analysis Set for Longitudinal Analysis. We will test each of the secondary endpoints with a 2-sided p-value against threshold of 0.05 (a 2-sided 5% alpha) with no further adjustment for multiplicity.

Further detail of the hypotheses tested is found in Section 10.

Figure 1 Primary and Secondary Gatekeeping Procedural Flow

Note: The hypothesis tests indicated above are to be performed on the endpoints which we have specified as primary and secondary, WOMAC A1 change from baseline at 26 (primary) weeks and also at 2, 4, 8, and 16 weeks.

7 Interval Windows

The study windows are presented in the Time and Events Schedule (CSP Section 1.1).

For analysis purposes, the baseline/screening evaluation is to be done within 30 days prior to the first injection; the first injection is considered to be day 0. The 2, 4, 8, 16 and 26 Week visits will occur in the time intervals (days) indicated in Table 2, below.

Table 2 Study Interval Windows

Analysis Visit Label	Nominal Study Visit	Study Interval
Baseline	Baseline/Screening	-30 to 0
2 Week	Day 14 ± 7 days	11 to 17
4 Week	Day 28 ± 7 days	21 to 35
8 Week	Day 60 ± 14 days	46 to 74
16 Week	Day 120 ± 14 days	105 to 134
26 Week	Day 180 ± 14 days	159 to 201

Note:

Day 0 is defined as the Study Day of first injection.

Baseline is defined as the last non-missing assessment prior to first injection.

Baseline must occur no more than 30 days after Screening.

8 Handling of Missing Data

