13.4.2 Secondary Endpoint Analyses

The secondary endpoints are the WOMAC A1 walking pain change from baseline at each post-baseline time point: 2, 4, 8, and 16 Week. Each of the secondary endpoints will be analyzed utilizing the primary longitudinal model described in the Primary Endpoint Analysis (Section 13.4.1). A gate-keeping procedure will be implemented to control the family-wise Type 1 Error (see Section 6.1), thus the secondary endpoints will be tested in sequence only provided as a statistically significant result was obtained in the previous test.

If any of the sensitivity analyses conducted on the primary endpoint produces results which differ substantially from the primary analysis, the sensitivity analyses will be repeated on all secondary endpoints.

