13.8 Additional Analyses

The tertiary endpoints will be analyzed as described below:

Walking Pain:

WOMAC A1 score mean change over 26 Weeks will be analyzed using the same longitudinal model and analysis sets as the primary endpoint. The mean changes in WOMAC A1 over 26 Weeks will be reported as the least squares means for treatment and the between treatment group difference will be estimated.

WOMAC A1 score at the 2, 4, 8, 16 and 26 Week time points will be analyzed with a similar longitudinal model to that of the primary endpoint; however, the dependent variable will become the observed value (rather than change).

WOMAC A1 score change from baseline area under the curve (AUC) will be analyzed using the trapezoidal rule to calculate the AUC for each subject. Data will be reduced to a single AUC result per subject then an appropriate between-treatment 2 sample

t-test will be conducted. If the AUC appear non-normal, then an additional t-test comparison will be done on log-transformed data.

Pain:

WOMAC A score at the 2, 4, 8, 16 and 26 Week time points will be analyzed with a similar longitudinal model to that of the primary endpoint; however, the dependent variable will become the observed value (rather than change) for the entire pain subscale.

WOMAC A score change (improvement) from baseline at the 2, 4, 8, 16 and 26 Week time points will be analyzed with a similar longitudinal model to that of the primary endpoint; however, the dependent variable will become the change from baseline for the entire pain subscale.

Pain, Stiffness and Physical Functioning:

Summary statistics for the total WOMAC score at the 2, 4, 8, 16 and 26 Week time points will be provided.

Summary statistics for the total WOMAC score change (improvement) from baseline at the 2, 4, 8, 16 and 26 Week time points will be provided.

Disease Activity:

Patient Global Assessment (PGA) at the 2, 4, 8, 16, and 26 Week time points will be summarized as tallies in each ordinal category (0 through 10).

Health Outcomes:

Summary statistics for the Physical and Mental Composite scores of the SF-12 outcomes at study defined time-points will be provided.

Rescue Medicine Consumption:

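### SAP 13.4.1 has no treatment-by-visit term, so the model does not estimate a 26-week difference and all visit-specific tests return the same result

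*SAP*

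**What the plan says.** SAP 13.4.1 specifies the primary model in full: change from baseline in WOMAC A1 as the response, "treatment (MONOVISC versus Saline) and visit (Week 2, Week 4, Week 8, Week 16, and Week 26) as fixed effects", subject as a random effect, visit as a class variable, an antedependence covariance and Kenward–Roger degrees of freedom. No interaction is listed.

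Other sections ask this model for visit-specific results:

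- **Primary decision (SAP 10):** "The adjusted means from this longitudinal model at 26 Weeks will be compared between treatment groups".
- **Gatekeeping (SAP 6.1), in the order 26, 16, 8, 4, 2 weeks:** "Each of these tests will be conducted utilizing the primary endpoint analysis on the Modified Intent to Treat Analysis Set for Longitudinal Analysis".
- **Secondary endpoints (SAP 13.4.2):** "Each of the secondary endpoints will be analyzed utilizing the primary longitudinal model described in the Primary Endpoint Analysis".
- **Tertiary mean change (SAP 13.8):** "WOMAC A1 score mean change over 26 Weeks will be analyzed using the same longitudinal model and analysis sets as the primary endpoint". Table 1 in SAP 2 adds this endpoint alongside the 26-week one because "interest lies in assessing the difference in the mean change from baseline in WOMAC A1 over the entire study period", so the two are meant to be different quantities.

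The protocol (11.6, 11.7, 11.10) also requires adjusted means at 26 weeks, but lists no fixed effects and so does not supply the term.

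**The concern.** With main effects only, the model forces the treatment difference to be the same at all five visits. The week-26 adjusted means differ between arms, but by a pooled amount to which weeks 2, 4, 8 and 16 also contribute. Under Protocol 8.7 the week-4 questionnaires are completed before the second injection, so both week 2 and week 4 reflect one injection only.

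Three things follow. A benefit that has disappeared by week 26 can be reported as a 26-week success. A benefit that builds after the second injection is diluted. The gatekeeping sequence has no content, because all five tests carry the same p-value and pass or fail together; the tertiary mean change repeats the same number again.

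The planned sensitivity analyses do not repair this. The autoregressive, Toeplitz and per-protocol repeats keep the same fixed effects, the covariate analysis adds only age, gender and baseline score, and SAP 13.7 adds only site and treatment-by-site. SAP 13.4.3 plans no further efficacy analysis of the primary and secondary endpoints.

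**Working it through.** **The plan's own figure.** SAP 12 assumes a difference of 0.6, SD 2.2, two-sided alpha 0.05 and 2:1 allocation, and reports 318 + 159 for 80% power. This reproduces: noncentral-t power at 318/159 is 80.02%. The calculation concerns a 26-week contrast with SE = 2.2 × √(1/318 + 1/159) = 0.214.

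**The algebra.** Under SAP 13.4.1, E[Y] = visit effect + β × treatment. The MONOVISC-minus-Saline difference at visit v is (visit v + β) − visit v = β for every v, whatever the covariance. Two fits to simulated trials with true effects −0.6, −0.6, −0.6, −0.3 and 0 confirm it. Generalized least squares with antedependence and missing visits gave −0.379 (SE 0.145, p = 0.009) at all five visits; a random-subject mixed model on another simulated trial gave −0.537 at all five. Adding treatment-by-visit to the first fit gave −0.467, −0.542, −0.829, −0.566 and −0.068, with week-26 p = 0.73.

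**What β averages.** With complete data the weights are w = V⁻¹1 / (1′V⁻¹1), where V is the 5 × 5 covariance of the visits. The documents give no correlations, so these are assumptions. With equal SD and uniform adjacent correlation r under antedependence, the week-26 weight is 1/(5 − 3r) and SE(β) = 0.214 × √[(1 + r)/(5 − 3r)].

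| Assumed covariance | Week-26 weight | Weeks 2 + 4 weight | SE(β) |
|---|---|---|---|
| r = 0.5 | 0.286 | 0.429 | 0.140 |
| r = 0.6 | 0.313 | 0.438 | 0.151 |
| r = 0.7 | 0.345 | 0.448 | 0.164 |
| r = 0.8 | 0.385 | 0.462 | 0.178 |
| SD rising 1.8 to 2.2; r = 0.8, 0.75, 0.65, 0.6 | 0.275 | 0.532 | 0.147 |

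**Consequences.** Write d for the assumed true improvements at weeks 2/4/8/16/26. The chance of final success is 1 − Φ(1.96 − w′d/SE). For example, with r = 0.5 and a fading effect, w′d = 0.286 × 0.6 + 0.143 × (0.6 + 0.6 + 0.3) = 0.386, and 1 − Φ(1.96 − 0.386/0.140) = 0.79.

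For the futility rule at 74/37, SE = 2.2 × √(1/74 + 1/37) = 0.443. The chance of exceeding 0.4 is 18% if the true week-26 difference is 0 and 67% if it is 0.6. Interim and final results are combined as bivariate normal with covariance (1/318 + 1/159) w′V e₂₆ (e₂₆ picks out week 26), treating the per-protocol and as-treated interim sets as the same subjects.

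| True profile d | w′d as written | Final success: as written / with interaction | Counting futility stop: as written / with interaction |
|---|---|---|---|
| Fading 0.6/0.6/0.6/0.3/0 | 0.35–0.40 | 50–79% / 2.5% | 13–17% / 1.5% |
| Building 0/0.1/0.3/0.5/0.6 | 0.25–0.30 | 39–57% / 80% | 32–43% / 59% |
| Constant 0.6 | 0.6 | 92–99% / 80% | 65–67% / 59% |
| No effect at any visit | 0 | 2.5% / 2.5% | not needed |

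Simulation of 20,000 trials agrees. With r = 0.5, fading gave 0.790 at the final analysis and 0.167 with the stop (interaction model: 0.026 and 0.016); building gave 0.571 and 0.431 (0.802 and 0.597).

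**The case against.** The best defence is that everyone knows what was meant. SAP 10, the ordered visit tests and the separate mean-change endpoint all presuppose visit-specific contrasts, and Table 1 in SAP 2 announces no change to the 26-week comparison. That is the natural reading of intent, and it stands. It does not rescue the text: SAP 13.7 counts an interaction as a fixed effect in its own right when one is wanted, and 13.4.1 names none.

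The magnitudes rest on chosen profiles. A milder build-up of 0.3/0.4/0.5/0.6/0.6 gives 74–92% power as written against 80% with the interaction, so there is often no loss; a constant effect favours the additive model. Both points stand.

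The covariance range is also too narrow. SAP 13.4.1 has a random subject effect as well as antedependence. A shared subject variance leaves the weights unchanged, so they follow the residual correlation. With a subject share of 0.3–0.6 and residual correlation 0–0.4 (again assumptions), week 26 carries only 20–26% and fading-effect success is 57–84%. This widens the range without changing direction.

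Some planned analyses do look at week 26 or avoid the additive model: the futility comparison (SAP 14.6, 14.7), the site ANOVA of week-26 data (SAP 13.6), the per-subject AUC t-test (SAP 13.8) and the by-visit summaries ("Effectiveness endpoints will be summarized at each protocol-specified evaluation time point on the Per Protocol Analysis Set for the time point", SAP 13). Only the futility rule affects the trial's course, and it reduces the harm without removing it. The others do not enter the success decision.

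**Conclusion.** The concern holds and must be fixed. The core is algebraic and needs no assumption: the model in SAP 13.4.1 cannot produce a treatment difference specific to week 26, which contradicts SAP 10, empties the gatekeeping in SAP 6.1 and makes the added mean-change endpoint a duplicate of the primary.

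Only the size of the consequence depends on assumptions: 318/159 with complete data, SD about 2.2, and the correlations and profiles above. The inflation concerns the week-26 null when earlier effects are non-zero; with no effect at any visit, error is 2.5% under both models at the final analysis. In the fading case the futility stop still leaves success about nine times as likely as with the interaction (13% against 1.5%) or more.

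**What to change.** In SAP 13.4.1, add treatment-by-visit as a fixed effect. Define the primary test as the MONOVISC-minus-Saline contrast at week 26 from that model, and the secondary tests as the contrasts at weeks 16, 8, 4 and 2.

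The per-protocol, covariance-structure, covariate and site analyses inherit the change. Carry it into the visit-wise tertiary models in SAP 13.8 as well (observed WOMAC A1, and WOMAC A score and change). State there that the 26-week mean change is the average of the visit contrasts, and with what weights.

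The cost is one model term and named contrasts, with no new data or patients. The sample size is unaffected because "the sample size was established based upon estimates for a t-test comparison of 26 week means for simplicity" (SAP 12). The price is precision if the effect is truly constant: the standard error is 0.214 instead of 0.140–0.178, and power is the planned 80% instead of 92–99%.
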